Clinical Investigational Plan Synopsis Study Name: Substrate-targeted Catheter Ablation to Treat Atrial Fibrillation Ver. 1.0 11MAR2015
Clinical Investigational Plan Synopsis	

Title:	Substrate-Targeted Catheter Ablation to Treat Persistent Atrial Fibrillation
Acronym:	AF Substrate Mapping and Guided Ablation
Purpose:	Evaluate the feasibility of substrate-targeted catheter ablation to treat Persistent AF
Objectives:	
Primary Objective
 
 Assess acute and long-term outcome of patient-tailored substrate-targeted ablation (Substrate) plus modified circumferential pulmonary vein ablation (Substrate+mCPVA) versus modified circumferential pulmonary vein ablation alone (mCPVA) 
Secondary Objective
 
 Map and characterize electrophysiological substrates during AF, including regular and fast activities, complex fractionated electrograms, wave front propagation directions, and fibrosis
Endpoints:	
Primary Endpoint
 
Twelve-month clinical success rate defined as
 
 Freedom from symptomatic AF off antiarrhythmic drug therapy assessed from the end of the 3 months blanking period to 12 months following the ablation procedure, documented by implantable loop recorder (ILR) monitoring or trans-telephonic (TT) ECG monitoring. 
Secondary Endpoint
 
 - Collect maps that identify substrates that could serve as mechanisms of AF maintenance, such as: 
 o Areas with fast but regular activities o Areas with consistent wave front propagation pattern o Areas with low P-P voltage o Areas with complex fractionated electrograms - Acute AF termination or significant AF cycle length slowing during RF application in ablation procedure - Inducibility of AF by programmed stimuli at the end of the ablation procedure before and after administration of Isoproterenol - Freedom from symptomatic atrial tachycardia and atrial flutter off antiarrhythmic drug therapy assessed from the end of the 3 months blanking period to 12 months following the ablation procedure, documented by ILR monitoring or TT ECG monitoring - Freedom from asymptomatic AF, atrial tachycardia, and atrial flutter off antiarrhythmic drug therapy assessed from the end of the 3 months blanking period to 12 months following the ablation procedure, documented by ILR monitoring or TT ECG monitoring - Need for a new ablation procedure - Need to prescribe antiarrhythmic drugs after the blanking period AF burden measured by ILR at follow-up visits

	Clinical Investigational Plan Synopsis Study Name: Substrate-targeted Catheter Ablation to Treat Atrial Fibrillation Ver. 1.0 11MAR2015
--	--

Clinical Investigational Plan Synopsis

[figure not shown]
Design:	
Prospective, single center, randomized, single-blind, controlled, 2-arm parallel group trial in Milan, Italy (Pr. [name], Targeted Research Center)
 
The total duration of the study is expected to be 24 months with ~12 months of enrollment.
 
Approximately 80 subjects suffering from persistent AF will be randomized in a 1:1 fashion to the following investigation arms:
 
 - Modified circumferential pulmonary vein ablation alone (mCPVA); - Substrate-targeted ablation guided by AF substrate mapping, followed by completion of modified circumferential pulmonary vein ablation (Substrate+ mCPVA) 
 • Ablate the areas that have fast and regular electrical activities, starting from the fastest cycle length (defined by Mean CL in the range of 120-250 milliseconds, and SD CL in the range of 1-30 milliseconds) • Ablate the areas that have consistent rotational or focal propagation pattern (defined by conduction velocity vectors) • Ablate the areas that comprises the slow conduction zone of possible arrhythmia circuits • If AF terminates during RF ablation, stimulation protocol will be used to examine if AF is re-inducible. If AF is re-inducible and physician decides to remap, mapping will be performed again for substrate-targeted ablation. If AF is not re-inducible, mCPVA will be completed 
Subjects will be followed up at 3, 6, 12 months.

Devices used:	
 - EnSite™ Velocity™ mapping system (CE marked) - Inquiry™ AFocusII™ diagnostic catheter (CE marked) - EnSite Velocity Research Platform consisting of: 
 o EnSite Velocity Research Display Workstation (CE marked) o EnSite Velocity Research Switch (OEM CE marked) o EnSite Velocity Research software (not CE marked) - Any commercially available Radiofrequency (RF) ablation system - Any commercially available irrigated tip RF ablation catheter (minimum 4 electrodes) - Any CE-marked EP diagnostic catheter (minimum 4 electrodes)
Study Population	Patients with persistent AF scheduled to undergo first or second time catheter ablation with approved standard indication by ESC/EHRA Guidelines
Inclusion/Exclusion Criteria	
Inclusion Criteria
 
 1. Age between 18 and 85 years 2. Persistent AF 3. Ability to provide informed consent for study participation and be willing and able to comply with study evaluations and follow-up schedule

Clinical Investigational Plan Synopsis

	
Exclusion Criteria
 
1. Two or more previous AF ablations2. Secondary AF3. Hyperthyroidism4. Left ventricular ejection fraction <30%5. NYHA functional class IV6. Left atrial area > 35 cm²7. Uncorrected severe valvular heart disease8. Contraindication to anticoagulation9. Presence of left atrial thrombus10. Recent (<6 Months) myocardial Infarction or unstable angina or coronary artery by-pass11. Thoracic surgery for congenital, valvular or aortic disease12. History of cerebrovascular accidents13. Pregnancy14. Significant comorbidities such as cancer, severe renal insufficiency requiring hemodialysis, severe obstructive lung disease, cirrhosis, with a life expectancy less than 2 years
Data Collection	
- Pre-procedure: Data collection per standard clinical practice for patients undergoing AF ablation- During-procedure: EnSite Velocity Study Backup DVDs, including 3D geometry of LA, contact maps collected by AFocus II catheter, electrograms, RF lesion locations, marker locations, electrode locations, user annotations, events of acute AF termination or significant CL slowing 
Post-procedure: AF recurrence documented by ILR or TT ECG monitoring

Clinical Investigational Plan Synopsis

1. Study Flow Chart

Clinical Investigational Plan Synopsis

2. Statistical analysis

In subjects with persistent AF, it is possible to demonstrate a one-year clinical difference among the two therapies with a significance level of 0.5 and a power of 0.80 using a Log-rank test in 38 subjects per group, estimated success of 50% and 80% in the control arm and mapping arm, respectively. The expected difference is based on extensive experience of the operators. Considering 5% drop-out rates, thus a total of 80 subjects will be included and assigned to either treatment group according to a randomization schedule stratified by the previous ablation procedures (none and one previous ablation procedure). Categorical and continuous variables are expressed as absolute and relative frequencies or as mean \pm SD or median (interquartile range [IQR]) as appropriate. Comparisons of continuous variables were done with a Student t-test or the Mann-Whitney U test as appropriate and binomial variables with chi-square or Fisher test. Long-term outcome was assessed, after a single ablation procedure, by Kaplan-Meier method and compared using the log rank test. A 2-tailed probability value of ≤ 0.05 was deemed significant. Statistical analyses were conducted using SPSS (SPSS v22, USA).

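### The acute endpoint pools AF termination with an undefined cycle-length slowing call that has more chances to be scored in the Substrate arm

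*Combined protocol and SAP*

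**What the plan says.** The Endpoints section lists, under Secondary Endpoint, "Acute AF termination or significant AF cycle length slowing during RF application in ablation procedure". The Data Collection section lists the same thing among the items stored from the procedure: "user annotations, events of acute AF termination or significant CL slowing". Neither place says how much slowing is significant, against which baseline, at which site, over what window, or who decides.

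The Design section sets the two lesion sets. Control is "Modified circumferential pulmonary vein ablation alone". The test arm is "Substrate-targeted ablation guided by AF substrate mapping, followed by completion of modified circumferential pulmonary vein ablation". The trial is described as "Prospective, single center, randomized, single-blind, controlled, 2-arm parallel group trial"; who is blinded is not stated.

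The primary objective covers acute as well as long-term outcome and compares Substrate+mCPVA with mCPVA alone. Section 2, Statistical analysis, gives generic methods: chi-square or Fisher for binary variables, and t-test or Mann-Whitney for continuous ones. It names no analysis for this endpoint, no adjustment for RF exposure and no common stage of the procedure at which the arms are compared.

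**The concern.** The endpoint joins two unlike things. Termination of AF is a hard event. Significant slowing is a judgement without a written standard, made in a procedure whose operator knows which lesions are being delivered and why. If AF cycle length fluctuates without treatment, some applications will coincide with a lengthening that someone could log as slowing.

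When a patient scores by having at least one such call, the probability of scoring rises with the number of applications. The Substrate arm has more of them by design. A pooled rate could therefore favour that arm to some degree even if the added lesions had no effect on AF.

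At stake is the acute half of the primary objective. This endpoint is one of two acute efficacy measures, the other being inducibility at the end of the procedure.

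**Working it through.** The plan states no rate, effect size or sample size for this endpoint, so it has no figure to reproduce. The check concerns how the scoring rule behaves.

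**Inputs from the documents**
- RF exposure, control: the mCPVA lesion set (Design).
- RF exposure, test arm: substrate lesions plus the mCPVA lesion set (Design).
- Patients: about 80 randomized 1:1, so about 40 per arm (Design).
- Two-sided significance level for analysis: 0.05 (Section 2).

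**Assumptions, because the documents are silent**
- Control applications *a* = 20 or 40; test-arm applications *b* = 1.5*a* or 2*a*.
- Chance of a spurious slowing call per application *q* = 0.1% to 5%, the same in both arms and independent between applications.
- No true effect of the added lesions.
- A patient scores if slowing is called at one or more applications.

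**Formula.** P(at least one chance call in *k* applications) = 1 − (1 − *q*)^*k*. The spurious gap is (1 − *q*)^*a* − (1 − *q*)^*b*.

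Worked example, *q* = 1%, 20 vs 40 applications: 1 − 0.99^20 = 18.2%; 1 − 0.99^40 = 33.1%; gap 14.9 points.

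| *q* | 20 vs 30 | 20 vs 40 | 40 vs 60 | 40 vs 80 |
|---|---|---|---|---|
| 0.1% | 2.0 vs 3.0 (gap 1.0) | 2.0 vs 3.9 (1.9) | 3.9 vs 5.8 (1.9) | 3.9 vs 7.7 (3.8) |
| 0.5% | 9.5 vs 14.0 (4.4) | 9.5 vs 18.2 (8.6) | 18.2 vs 26.0 (7.8) | 18.2 vs 33.0 (14.9) |
| 1% | 18.2 vs 26.0 (7.8) | 18.2 vs 33.1 (14.9) | 33.1 vs 45.3 (12.2) | 33.1 vs 55.2 (22.1) |
| 2% | 33.2 vs 45.5 (12.2) | 33.2 vs 55.4 (22.2) | 55.4 vs 70.2 (14.8) | 55.4 vs 80.1 (24.7) |
| 5% | 64.2 vs 78.5 (14.4) | 64.2 vs 87.1 (23.0) | 87.1 vs 95.4 (8.2) | 87.1 vs 98.3 (11.2) |

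Entries are percentages of patients, control vs Substrate. Gaps are in percentage points, computed before rounding.

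**What the table shows**
- For *q* from 0.5% to 5% the gap runs from 4.4 to 24.7 points. At *q* = 0.1% it runs from 1.0 to 3.8.
- With equal applications (20 vs 20) the gap is zero at every *q*, so unequal exposure is the source.
- If *q* varies between patients, with the same distribution in both arms, the gap changes in size but not in sign: for every patient (1 − *q*)^*a* ≥ (1 − *q*)^*b* when *b* > *a*.

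**Effect on a test.** With 40 per arm and a normal approximation for two proportions, the probability of a two-sided 0.05 result favouring the Substrate arm should be 2.5% under no effect. Over these exposure patterns it is 9% to 33% at *q* = 0.5% and 13% to 68% for *q* from 1% to 5%.

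**The case against.** **No counting rule is written.** This is correct. Scoring at any application is inferred from the wording. The events are stored alongside lesion locations, which would also fit a descriptive, lesion-level use. A rate per application would not have this dependence on the number of applications. The gap in the plan is therefore that the rule is missing, and the bias follows on the natural reading of it.

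**Added lesions are the intervention.** This also stands. The primary objective compares two strategies, and extra RF may have real effects. A reader might infer that any advantage for the Substrate arm would be chance alone. The documents do not support that. The mechanism applies to an undefined slowing call, not to termination, and a real effect could coexist with it. The problem is that the pooled rate cannot tell the two apart.

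**Remapping.** A reader might add remap rounds to the extra chances, since the Design section says "If AF is re-inducible and physician decides to remap, mapping will be performed again for substrate-targeted ablation". That sentence applies only after AF has terminated during RF and then proved re-inducible. Such a patient has already scored through termination, so remap rounds add nothing to an at-least-once count.

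**AF needed for mapping in one arm only.** A reader might infer this from the Design section. It is not established: map collection (Endpoints) and contact maps (Data Collection) are listed without restriction by arm.

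**It is a secondary endpoint in the synopsis of a feasibility study.** True, and this limits the weight of the point. But the trial is randomized and its primary objective names acute outcome as a between-arm comparison, so the endpoint needs a definition that can carry one.

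**Conclusion.** The concern holds in a limited form. The lack of a definition for slowing, its pooling with termination, and the additional RF lesions in the Substrate arm are all in the text. From these it follows that, on the any-application reading and with any nonzero chance rate, the pooled rate can favour the Substrate arm partly without an effect.

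The direction follows from the design, but the size does not. The 4 to 25 points rest on assumed chance rates of 0.5% to 5%, assumed application counts and independence between applications; at 0.1% the gap falls to about 1 to 4 points. No single scenario, such as a doubling from 40 to 80 applications, should be quoted as the expected bias.

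The 12-month primary endpoint and its sample size are untouched. This should be corrected, but it does not threaten the main result.

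**What to change.** Split the endpoint in two.

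1. **AF termination during RF**, reported on its own as a whole-strategy outcome, as a proportion of patients who are in AF at the start of RF, with the same denominator rule in both arms. The inclusion criteria require persistent AF but not AF at the procedure, and a patient in sinus rhythm cannot terminate or slow.
2. **Change in AF cycle length**, as one continuous value per patient: mean AF cycle length at one pre-specified reference site before the first RF lesion, versus the last AF recording before termination or the end of RF. Calculate it from the stored electrograms by a fixed rule set before arm-level results are seen. Compare the arms with the t-test or Mann-Whitney test already planned. One value per patient removes the dependence on the number of calls.

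Drop the slowing event from the between-arm comparison. State in the plan that both measures compare the two strategies, and that neither separates mapped targeting from the extra RF that comes with it.

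**Cost.** The change needs endpoint wording and a fixed calculation; it needs no new patients or visits. The Data Collection section lists electrograms on the backup DVDs, but does not promise a reference-site recording at both time points, so its availability in both arms must be secured. The more favourable pooled rate would no longer be reported as an efficacy result.

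### Does the short post-procedure data list leave the primary log-rank event impossible to score?

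*Combined protocol and SAP*

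**What the plan says.** The document is a synopsis. Four parts bear on this point.

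- **Endpoints row, primary:** the definition reads "Freedom from symptomatic AF off antiarrhythmic drug therapy assessed from the end of the 3 months blanking period to 12 months following the ablation procedure". Detection is through the ILR or trans-telephonic ECG.
- **Endpoints row, secondary:** these include "Freedom from asymptomatic AF, atrial tachycardia, and atrial flutter off antiarrhythmic drug therapy", "Need for a new ablation procedure" and "Need to prescribe antiarrhythmic drugs after the blanking period", as well as AF burden by ILR, tachycardia and flutter, and inducibility.
- **Data Collection row:** the only post-procedure entry is "Post-procedure: AF recurrence documented by ILR or TT ECG monitoring".
- **Section 2 (Statistical analysis):** "Long-term outcome was assessed, after a single ablation procedure, by Kaplan-Meier method and compared using the log rank test". The sample size rests on "estimated success of 50% and 80% in the control arm and mapping arm, respectively", and randomization is "stratified by the previous ablation procedures (none and one previous ablation procedure").

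The Design row sets visits at 3, 6 and 12 months and calls the trial single-blind. Section 1 (Study Flow Chart) has a heading, but its content is not in the text available for review.

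**The concern.** Scoring the primary endpoint takes three facts about each patient after month 3: whether AF was documented, whether it was symptomatic, and whether the patient was on an antiarrhythmic drug. The Data Collection entry supplies only the first. An implantable recorder also picks up silent AF, which the plan assigns to a secondary endpoint. A patient kept on drugs without recurrence fails the primary endpoint but would look like a success on the listed data.

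Section 2 does not close the gap. It names the test but not the event, and it does not say whether a repeat ablation is a failure, a censoring time or ignored. The reference to a single procedure also needs interpreting, because patients with one previous ablation are eligible.

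Drug restart and re-ablation are clinicians' decisions, and the operator knows the arm. A scoring rule left open could therefore favour either arm. The documents give no evidence that it would.

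**Working it through.** **1. The plan's own figure.** Inputs from section 2: success 50% and 80%, power 0.80, log-rank test, 38 per group, 5% dropout, two-sided 0.05. (The sample-size sentence prints the level as 0.5. The figure reproduces at 0.05, the level given later in the same section. That is a separate matter.)

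- Hazard ratio = ln(0.80)/ln(0.50) = 0.322.
- Schoenfeld events = 4 × (1.960 + 0.842)² / (ln 0.322)², which rounds up to 25.
- Mean event probability = (0.50 + 0.20)/2 = 0.35, so 25/0.35 = 71.4 patients, about 36 per group. A pooled comparison of proportions gives 39. The stated 38 lies between.
- 76/0.95 = 80 in total, as stated.

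The sizing is expressed as success, the term the Endpoints row defines. That row therefore fixes what the curve should estimate.

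**2. Is the Data Collection row meant to be complete?** Compare it with the endpoints.

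| Endpoint in the Endpoints row | Named in the Data Collection row? |
|---|---|
| Documented AF | Yes |
| Symptom status of AF | No |
| Antiarrhythmic drug need | No |
| New ablation | No |
| Tachycardia and flutter | No |
| AF burden by ILR | No |
| Inducibility at end of procedure | No |

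The last three are plainly intended to be measured and are missing too. The row is a summary, so absence from it is weak evidence that an item goes uncollected.

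**3. What would be lost if the curve were built from that row alone?** All shares here are assumptions; the documents give none. The figures come from 5,000 simulated trials per setting: 38 per arm, constant hazards over months 3 to 12, censoring at month 12. Base power is 80.6%.

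- Asymptomatic AF counted as failure in a share *a* of successes gives apparent success S(1 − a).
- Drug-only or re-ablation-only failures unseen, as a share *f* of failures, give 1 − (1 − S)(1 − f).

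| Setting | Apparent success | Power |
|---|---|---|
| a = 10% / 20% / 30% | 45 v 72 / 40 v 64 / 35 v 56 | 70 / 56 / 46% |
| f = 10% / 20% / 30% | 55 v 82 / 60 v 84 / 65 v 86 | 73 / 66 / 58% |
| a = f = 20% | 0.60 × 0.8 = 48 v 0.84 × 0.8 = 67 | 41% |
| f = 30% control, 10% Substrate | 65 v 82 | 39% |
| f = 10% control, 30% Substrate | 55 v 86 | 87% |

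These losses are real under their premise. The premise is that the analyst ignores the definition of success and the drug and re-ablation data that the secondary endpoints call for.

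**4. The repeat-ablation gap.** It matters only for a patient re-ablated after blanking with no earlier symptomatic AF and no drug use. For illustration, take the expected failures: 0.50 × 38 = 19 in control and 0.20 × 38 = 7.6, rounded to 8, in the mapping arm. The log-rank p is 0.008.

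| Failures recoded (control, Substrate) | p, censored | p, event-free |
|---|---|---|
| 4, 2 | 0.015 | 0.021 |
| 4, 0 | 0.051 | 0.079 |

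The balanced case stays clearly below 0.05. Only a wholly one-sided split reaches the threshold.

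**5. The obvious remedy.** Suppose every repeat ablation counted as a primary failure, and this turned 5% or 10% of successes into failures in both arms (assumed).

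- At 5%, success becomes 0.50 × 0.95 = 47.5% v 0.80 × 0.95 = 76%. Power is about 74% by simulation, 77% by Schoenfeld.
- At 10%, success becomes 45% v 72%. Power is about 70% by either method.

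**The case for a change.** The strongest case for a change rests on symptom status. It decides whether an episode belongs to the primary or a secondary endpoint. Unlike drug need and new ablation, it is not an endpoint in its own right, and the available text gives no method for linking symptoms to a recorded episode. Visits are months apart, so symptoms not noted at the time may not be recoverable. Separately, even with every item on file, section 2 leaves event and censoring rules to the analyst, and a rule chosen after results are seen carries less weight.

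Both observations are accurate as descriptions of the text. They do not show that the data will be missing. Separate endpoints for symptomatic and asymptomatic arrhythmia cannot be reported unless episodes are classified, and the flow chart, the natural place for visit-level items, cannot be counted as silent when its content is not available. On scoring, the Endpoints row already implies the event: first symptomatic AF or drug use after blanking. With second-time patients eligible, the single procedure can only sensibly mean the study procedure. What stands is that the wording is sparse and that re-ablation without an earlier failure has no stated rule.

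**Conclusion.** The concern does not call for a change. The Data Collection row is narrower than the primary endpoint and section 2 is brief. But an analyst following the plan would score the success defined in the Endpoints row, using data that the listed endpoints already require. This is missing detail that would be filled sensibly.

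The power losses, down to 39% to 41%, should not be attributed to the plan, because nothing in it says the curve is built from AF recurrence alone. The remaining ambiguity over repeat ablation is small when the patients affected are balanced between arms (p of 0.015 to 0.021 against 0.008).

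Settling it by counting all repeat ablations as failures is a trade-off with no clear gain. It would move a secondary endpoint into the primary event, bring in re-ablation for flutter or tachycardia, and detach the 50% and 80% assumptions from the event analysed.

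This conclusion assumes that symptom status, drug use and repeat procedures are recorded, as the endpoints imply. If the flow chart or the case report form showed otherwise, the question would reopen.

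### The sample-size statement gives a significance level of 0.5, which conflicts with the 0.05 threshold in the same section and does not yield 38 per group

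*Combined protocol and SAP*

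**What the plan says.** Section 2 (Statistical analysis) of the Clinical Investigational Plan Synopsis is the only statistical text in the plan. It states that a one-year difference between the arms can be shown "with a significance level of 0.5 and a power of 0.80 using a Log-rank test in 38 subjects per group", with "estimated success of 50% and 80% in the control arm and mapping arm, respectively". It then allows for drop-out: "Considering 5% drop-out rates, thus a total of 80 subjects will be included". The Design row of the synopsis gives 1:1 allocation of approximately 80 subjects.

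Later in Section 2 comes the rule for declaring significance: "A 2-tailed probability value of ≤ 0.05 was deemed significant". That rule follows directly after the statement that long-term outcome is compared by the log-rank test.

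The sample-size sentence does not say whether its alpha is one- or two-sided, and does not name the formula or software behind the 38.

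**The concern.** The section carries two type I error rates for the same log-rank comparison, 0.5 and 0.05. If 0.5 were the true design input, 38 per group would be about three times what is needed. If 0.05 were the true input, the sample-size statement is misprinted. Either way, the printed alpha, power and sample size cannot all be right together.

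Alpha is the most basic operating characteristic of a randomised comparison, and this sentence is the only place where the plan justifies its size. An ethics committee or statistician who tries to reproduce the 38 from the printed inputs will fail. Taken at face value, the sentence describes a design that would declare a difference half the time when there is none.

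**Working it through.** **Inputs** (Section 2 unless noted): one-year success 50% in the control arm and 80% in the mapping arm; power 0.80; log-rank test; 38 per group; 5% drop-out; 80 in total; 1:1 allocation (Design row). Alpha is printed as 0.5 for sizing and 0.05 two-tailed for testing.

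**Derived quantities.** Assuming proportional hazards and follow-up of every subject to one year:

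- Hazard ratio = ln(0.8)/ln(0.5) = 0.322, so ln(HR) = −1.133.
- Mean event fraction = (0.50 + 0.20)/2 = 0.35, so 38 per group gives 76 × 0.35 = 26.6 expected events.
- (z for alpha + z for power)² is (0.674 + 0.842)² = 2.299 at two-sided 0.5, and (1.960 + 0.842)² = 7.849 at two-sided 0.05.

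**Sample size as printed, two-sided alpha 0.5.**

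- Schoenfeld: events = 4 × 2.299/1.133² = 7.16; per group = 7.16/(2 × 0.35) = 10.2.
- Freedman: events = 2.299 × [(1 + 0.322)/(1 − 0.322)]² = 2.299 × 1.950² = 8.74; per group = 8.74/0.70 = 12.5.

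Rounded up, that is 11 and 13 per group. If whole events are taken first (8 and 9), the figures are about 12 and 13.

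**Other formulas and the other alpha** (per group, 80% power):

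| Method | Two-sided 0.5 | Two-sided 0.05 |
|---|---|---|
| Schoenfeld | 10.2 | 34.9 |
| Freedman | 12.5 | 42.6 |
| Exponential hazards | 12.3 | 41.3 |
| Two proportions, pooled | 11.0 | 38.5 |
| Two proportions, continuity-corrected | 17 | 45 |
| Arcsine | 11.1 | 37.9 |

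Reading 0.5 as one-sided makes matters worse: those formulas then give about 4 to 9 per group. No version at 0.5 comes near 38. At two-sided 0.05 the formulas run from 35 to 45, with 38 inside the range.

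**Power with 38 per group (26.6 events).**

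- Schoenfeld: √26.6 × 1.133/2 = 2.923. Subtracting 0.674 gives power 0.988 at alpha 0.5; subtracting 1.960 gives 0.832 at alpha 0.05.
- Freedman: √26.6/1.950 = 2.646. The same steps give 0.976 and 0.753.
- Simulated log-rank test, exponential times, 20,000 runs per setting: about 0.99 at alpha 0.5, and 0.80 to 0.81 at two-sided 0.05 across repeated simulations.

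**Alpha implied by 38 per group and 80% power.** Working backwards, Schoenfeld gives z = 2.923 − 0.842 = 2.081, a two-sided alpha of 0.037. Freedman gives z = 2.646 − 0.842 = 1.804, a two-sided alpha of 0.071. The two values lie either side of 0.05 and nowhere near 0.5.

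**Drop-out.** 2 × 38 = 76, and 76/0.95 = 80, which matches the stated total.

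**The case against.** The best defence is that this is an obvious misprint with no consequence. The correct threshold stands in the same section, only that threshold governs the test, and the calculation was evidently not done at 0.5. Sample size, drop-out allowance and analysis would all be unchanged. That is accepted as far as it goes: the planned test is not mis-specified, and the 50% false-positive reading applies to the sample-size sentence, not to the decision rule. It does not make the sentence correct. It is the plan's only sample-size justification, and it is wrong as printed.

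A second objection is that 38 does not pin down two-sided 0.05 uniquely. The sizing sentence gives no sidedness, and the two closed-form log-rank formulas at two-sided 0.05 give 34.9 and 42.6 rather than 38. The nearest closed-form matches are two-proportion formulas (37.9 and 38.5), and a continuity-corrected two-proportion calculation at one-sided 0.05 gives 37. This stands in part. The figures show that 38 agrees with two-sided 0.05 and cannot be squared with 0.5; they do not show which method was used. The simulated log-rank power, and the two-tailed 0.05 already in the plan, are what make two-sided 0.05 the natural reading.

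A dropped zero in the text as reproduced cannot be wholly excluded. The figures 0.80 and 0.05 are intact in the same section, so this is unlikely, but a look at the signed copy would settle it.

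**Conclusion.** The point holds. The design alpha of 0.5 contradicts the plan's own two-tailed threshold by a factor of ten and does not produce 38 per group: it would call for about 11 to 13 under the log-rank formulas, and at most 17 under any formula tried. With 38 per group it would give about 98–99% power instead of 80%. Replacing it with two-sided 0.05 restores agreement between alpha, power, sample size and the total of 80, with simulated log-rank power of about 0.81.

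This rests on proportional hazards (exponential times in the simulation), complete one-year follow-up of the 76 subjects, and the 50% and 80% success rates as given. The rejection of 0.5 does not depend on the choice of formula. The closeness of 38 to its target does: at two-sided 0.05, power is 83% by Schoenfeld, 79% by two proportions and 75% by Freedman.

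**What to change.** In the sample-size sentence of Section 2, replace the significance level of 0.5 with a two-sided significance level of 0.05, in line with the testing threshold in the same section. Keep 38 per group and 80 in total.

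While the sentence is open, it would help to name the formula or software that produced the 38, because the standard methods at two-sided 0.05 range from 35 to 45 per group and a reader cannot tell which was used.

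The required change is one figure and a statement of sidedness. It does not affect recruitment, the planned analysis or the conduct of the trial.

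### Randomisation is stratified by previous ablation, but the log-rank test named for the outcome ignores the strata, so it is conservative and less powerful than a stratified test if previous ablation is prognostic

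*Combined protocol and SAP*

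**What the plan says.** Section 2 (Statistical analysis) plans 80 subjects, assigned "according to a randomization schedule stratified by the previous ablation procedures (none and one previous ablation procedure". The Study Population row of the synopsis admits first and second ablations, and the exclusion criteria rule out only patients with two or more, so both strata can be enrolled.

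The same section assesses long-term outcome "by Kaplan-Meier method and compared using the log rank test". The sample-size sentence also relies on "a power of 0.80 using a Log-rank test". Neither sentence mentions strata, and no other part of the document adjusts for previous ablation.

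**The concern.** Previous ablation is the only factor the sponsor chose to stratify on. If it is prognostic, balancing the arms within each stratum removes part of the chance variation in the treatment comparison. A plain log-rank test pools all patients and computes its variance as if that variation were still there. The variance is then too large, the p-value tends to be too large, and power is lost relative to a test that uses the strata.

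The trial has little power to spare. At the planned success rates, 80 subjects give 40 × 0.5 + 40 × 0.2 = 28 events before drop-out, and the assumed 30-point difference rests on the operators' experience. Silence on the strata also leaves the choice between the two tests open until the data have been seen.

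**Working it through.** **Inputs from the plan** (Section 2 unless noted)
- Success: "estimated success of 50% and 80% in the control arm and mapping arm, respectively".
- Sample size: "38 subjects per group" before drop-out. "Considering 5% drop-out rates, thus a total of 80 subjects will be included".
- Test level: "A 2-tailed probability value of ≤ 0.05 was deemed significant". The sample-size sentence prints 0.5 instead, which is a separate inconsistency.
- Allocation 1:1 (Design row). Outcome window from month 3 to month 12 (Endpoints row).

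**The plan's own figure**
- Hazard ratio = ln(0.8)/ln(0.5) = 0.322. Mean event fraction = (0.5 + 0.2)/2 = 0.35.
- Schoenfeld, two-sided 0.05, power 0.80: 4 × (1.960 + 0.842)² / (ln 0.322)² = 24.4, so 25 events. Then 25/0.35 = 71.4 patients, or 36 per group.
- Comparison of two proportions (pooled variance): 39 per group.
- The stated 38 lies between these. At the printed level of 0.5, Schoenfeld would need only about 12 per group, so 0.05 is evidently meant.
- Drop-out: 76/0.95 = 80, as stated.

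**Assumptions, because the documents give no figures**
- Share p of patients with one previous ablation: 20%, 30% or 50%.
- Between-stratum hazard ratio k: 1 (not prognostic), 1.5, 2, 3 or 5.
- Exact 1:1 balance within each stratum.

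**Simulation**

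Times are exponential, with the outcome window scaled to length 1.
- The control hazard λ solves (1−p)·exp(−λ) + p·exp(−kλ) = 0.5.
- The within-stratum treatment hazard ratio h solves (1−p)·exp(−λh) + p·exp(−kλh) = 0.8, with h = 1 under the null.

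Overall success therefore stays at 50% and 80% in every power scenario. The test statistic is z = Σ(O−E)/√ΣV, with rejection if |z| > 1.96. The stratified version computes O−E and V within each stratum and then adds them. There were 76 patients and 20,000 runs per cell. The Monte Carlo standard error is about 0.15 points for type I error and 0.3 points for power.

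| k | p | Type I error %, plain / stratified | Power %, plain / stratified |
|---|---|---|---|
| 1 | 20% | 5.1 / 5.2 | 80.1 / 80.2 |
| 1 | 30% | 5.4 / 5.3 | 80.5 / 80.2 |
| 1 | 50% | 4.8 / 4.9 | 80.8 / 80.8 |
| 1.5 | 20% | 4.9 / 5.1 | 81.1 / 81.2 |
| 1.5 | 30% | 4.9 / 5.1 | 80.4 / 80.8 |
| 1.5 | 50% | 5.2 / 5.5 | 80.5 / 80.9 |
| 2 | 20% | 4.9 / 5.4 | 81.6 / 82.6 |
| 2 | 30% | 4.5 / 5.1 | 80.9 / 81.9 |
| 2 | 50% | 4.5 / 5.0 | 81.7 / 83.0 |
| 3 | 20% | 3.9 / 5.2 | 81.3 / 84.3 |
| 3 | 30% | 3.5 / 4.9 | 81.9 / 85.2 |
| 3 | 50% | 3.7 / 5.3 | 81.8 / 84.8 |
| 5 | 20% | 2.7 / 5.3 | 83.9 / 90.4 |
| 5 | 30% | 2.5 / 5.4 | 83.4 / 90.6 |
| 5 | 50% | 2.3 / 5.3 | 83.6 / 89.0 |

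Power gained by stratifying the test is at most 0.4 points at k = 1.5, 1.0-1.3 at k = 2, 3.0-3.3 at k = 3 and 5.4-7.2 at k = 5.

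**Check with 80 patients and 5% drop-out** (shares of 30-50%)
- k = 2: type I error 4.3-4.5% plain against 5.0-5.1% stratified; power 0.82 against 0.83.
- k = 3: type I error 3.4-3.6% against 5.3%; power 0.83 against 0.86.

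**The case against.** - **Planned power is not breached.** The plain test keeps 80.1-83.9% power in every cell of the table. The loss is only relative to the better test, and a conservative p-value is still a valid one. This stands, and it limits the point to efficiency.
- **The larger losses need strong prognosis.** With overall control success fixed at 50% and a share of 30-50%, k = 2 means control success of 57-62% in first-ablation patients against 33-38% in second-ablation patients. For k = 3 the figures are 61-68% against 23-32%, a gap of 36-38 points. Nothing in the documents supports or rules out gaps of this size. This stands, and it is why the results are given as a range.
- **The conservatism depends on balance within strata.** The plan gives no blocks or block size. With simple, unblocked allocation (80 patients, 5% drop-out, 8,000 runs per cell) the plain test's type I error was 4.7-5.4% for k from 1.5 to 4. This stands for the type I error. However, balance within strata is the ordinary purpose of a stratified schedule, and the stratified test was still more powerful at k = 2 and above without blocking.
- **The plan is silent; it does not say the test is unstratified or call it primary.** The Endpoints row describes a twelve-month success rate, and Section 2 also assigns binomial variables to chi-square or Fisher tests. True, but the sample size is built on a log-rank test, and a log-rank test with no strata named is naturally read as a plain one. If a stratified test is intended, the plan needs to say so.

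**Conclusion.** The concern holds. The design stratifies by previous ablation, and the analysis as written does not use it. If the factor is prognostic and the arms are balanced within strata, the plain log-rank test is conservative and gives up power that the stratified test would keep. The size is modest at moderate prognostic strength and grows with it, and there is no material difference if the factor is not prognostic. Type I error is not inflated, and the planned sample size stands. The direction is secure. The size rests on the assumed share and prognostic strength, exponential times, and 1:1 balance within strata. The change is worth making because the factor must already be known at randomisation and the trial expects only about 28 events.

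**What to change.** In Section 2, state that the primary comparison is a log-rank test stratified by previous ablation (none/one), two-sided at 0.05. That clause alone cures the mismatch. It is also advisable to report a hazard ratio with its confidence interval from a Cox model stratified by the same factor, and to keep the plain log-rank test as a sensitivity analysis.

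The cost is about one sentence. There are only two strata, and neither the design, the data collection nor the sample size changes. The sentence should be added before outcome data are examined by arm.
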